3.0 STUDY DESIGN

3.1 Study protocol description

The objective of this study is to test three new PDT regimens for actinic keratoses (AK) of the face that promise to greatly reduce the pain normally associated with the procedure. The new regimens, called A, B, and C, respectively, will use a photosensitizer (aminolevulinic acid, 10% ALA gel, Ameluz®) and an activating red light illumination source (BF-RhodoLED® red light panel, 635 nm) from Biofrontera, Inc. Both ALA gel and the 635 nm light source from Biofrontera are currently FDA-approved for broad-area PDT treatment of AK. The approved FDA treatment (standard regimen) specifies that ALA gel be applied topically and left on for 3 hours, followed by exposure to red light for 10 minutes. Here, the timing for topical ALA gel incubation will be shortened, to test the hypothesis that pain experienced during red light illumination can be significantly reduced while still preserving the efficacy of the procedure in terms of lesion clearance (pain and efficacy are primary endpoints). Safety and patient satisfaction will also be assessed (secondary endpoints). Timing for the 3 regimens will be as follows: **A**, ALA gel for 10 min, then red light for 20 min while ALA gel is left incubating. **B**, ALA gel for 20 min, then red light for 10 min while ALA gel is left incubating. **C**, ALA gel for 60 min, then red light for 10 min. We hypothesize that each of the new regimens will cause significantly less pain than the

current standard regimen for ALA gel/red light PDT, and that a lesion clearance response will be achieved that is similar (i.e., statistically non-inferior) to the standard treatment regimen.

3.2 Number of subjects

A total of 30 patients will be needed to complete the study.

3.3 Replacement of subjects

If a study subject withdraws for any reason, up to 3 months after the start of this study, then a new subject can be recruited in his/her place.

3.4 Expected duration of therapy, and duration of subject participation

The total duration of the subject participation in this study will be approximately 4 months and will include 3-4 clinic visits and a screening procedure (either in person or via telephone interview).

4.0 PATIENT SELECTION

4.1 Inclusion Criteria

Males or females, must be at least 18 years of age, with a minimum of 10 actinic keratoses lesions on the face. A total of 10 subjects will be enrolled for each of the study arms A, B, and C. The study will be conducted at the Cleveland Clinic.

4.1.2 Female subjects must not become pregnant during the study

The effects of 5-aminolevulinic acid (Ameluz®) on the human fetus are unknown. For this reason, women of child-bearing potential must agree to use contraception. *However, it should be noted that the vast majority of patients with chronic sun-induced AK lesions are beyond the age of menopause.* Should a woman become pregnant or suspect that she is pregnant while she is participating in this study, she should inform the treating physician immediately.

4.1.3 Subjects must be able to understand and willing to sign a written informed consent document.

4.2 Exclusion Criteria

- 4.2.1 Pregnant or nursing.
- 4.2.2 Using any topical treatment on their AKs; must stop at least one month prior.
- 4.2.3 Currently undergoing treatment for other cancers with medical or radiation therapy.
- 4.2.4 Patients with a known hypersensitivity to 5-aminolevulinic acid or any component of the study material.
- 4.2.5 Patients with history of a photosensitivity disease, such as porphyria cutanea tarda.

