1.0 Specifications for Ameluz

2.0 Specifications for the BF-RhodoLED®red light source

3.0 Post-PDT Side Effects Journal

4.0 Patient Satisfaction Questionnaire

1.0 Introduction

1.1 Background and Significance

Actinic keratoses (AK), are dysplastic precancerous lesions of the skin with potential to develop into squamous cell carcinoma. AKs are extremely common and are typically observed in sun-damaged skin of Caucasian individuals. It is important to treat AKs because of the possibility that 2-5% of them may evolve into squamous cell carcinoma (SCC). Progression of AK to SCC is even higher in immunosuppressed patients, e.g. organ transplantation recipients. Amongst currently available treatments for widespread AK that include surgical (cryotherapy, scalpel excision) and medicinal approaches (topical 5-fluorouracil, imiquimod, diclofenac cream) approaches, a relatively new modality called photodynamic therapy (PDT) has several distinct advantages [1]. PDT is a method in which a topical drug such as aminolevulinic acid (ALA) or methyl-ALA is applied to AK lesions, where it is taken up selectively by precancer cells [2]. Within the cells, ALA is converted into a photosensitizer (protoporphyrin IX, PpIX) within mitochondria, whereupon a strong visible light is used to activate the PpIX, triggering photochemical reactions such as the generation of reactive oxygen species that kill the precancer cells. PDT excels as a modality to treat widespread areas of field cancerization, and it has the additional advantages of minimal down time and rapid recovery, lack of scarring, lack of pigmentary changes, and repeatability [3]. However, a limiting factor with all current versions of aminolevulinate-based PDT is *stinging pain* that patients often have to endure during illumination [4]. This pain is proportional to the amount of the target photosensitizer (PpIX) that is present in the skin prior to the start of illumination. Pain is a frequent occurrence in patients who receive PDT with standard protocols currently approved by the FDA, all of which required an ALA incubation period of many hours, i.e., 14-18 hr with Levulan Kerastick (20% ALA), 3 hr with Metvixia (16% methyl-ALA), and 3 hr for Ameluz (10% ALA nanoemulsion). Metvixia and Ameluz, also require that an occlusive dressing be applied to enhance penetration. Metvixia is no longer available in the US, leaving Ameluz and Levulan as the only two viable options for dermatologists providing PDT in the United States. Ameluz has generated significant interest due its properties as lipid-based nanoemulsion that exhibits superior uptake into AK lesions [5].

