1.2 Scientific rationale for the proposed study

The proposed pilot study will simultaneously address the 3 current drawbacks of PDT using Ameluz and red light, which are: (1) pain during illumination, (2) lengthy incubation periods, and (3) the inconvenience of plastic wrap occlusion.

The rationale for this study is based upon recent findings and observations from another version of PDT technology for actinic keratosis, namely, 5-ALA (Levulan) and blue light, in which a short-incubation regimen was developed and shown to provide excellent efficacy while generating minimal pain during illumination [6, 7]. The principle exploited by those studies is that conversion of ALA to PpIX begins as soon as ALA is applied to the lesions [8]. Thus PpIX can be photoactivated, even at low levels, by illumination with blue or red light, thereby destroying mitochondria and triggering a somewhat delayed yet highly effective inflammatory-immunological response to eliminate the lesions [9]. Previously, in developing a ‘painless blue light protocol’, our group compared two Levulan/blue light protocols in a bilateral comparative format (each patient serving as his/her own control). On one side, AK lesions were treated using the shortest drug incubation time that was known to produce significant lesion clearance (1 h ALA incubation), followed by illumination for 16 min 40 sec (as in the standard FDA-approved blue light protocol). This produced a pain level, on average, ~5 on a 1-10 visual-analog scale. On the contralateral side of the face, AK lesions were treated with immediate (simultaneous) illumination, in which 20% ALA solution was applied and then blue light was shone for either 30 min, 45 min, or 60 min. In all three of these timed cohorts, patients reported very low pain levels (~1 out of 10), and yet they developed erythema and lesion clearance rates at 3 month that were similar (statistically non-inferior) to the ‘traditional’ 1 hr ALA incubation period [7]. This study demonstrated that good treatment efficacy can still be obtained even when pain is minimized using an ALA short-contact approach.

In the current study, we will seek to translate the findings observed with 5-ALA/blue light (above), into a regimen with 10% ALA gel and red light, and assess its feasibility.

1.3. Rationale for the experimental design.

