The experimental strategy is to examine short-contact Ameluz/red light protocols in a well-established PDT clinic, to explore pain reduction and treatment efficacy using an FDA-approved PDT drug (Ameluz) and light source (BF-RhodoLED® red light panel) under conditions that have been modified to be sub-maximal (i.e., using shorter than usual drug-incubation times). Our hypothesis is that patient comfort will be greatly improved, yet an acceptable treatment efficacy will be maintained. We plan to invite patients who are already scheduled to undergo PDT treatment in [name] clinic for actinic keratoses of the face to participate in the study.

The following scientific questions will be asked and addressed in a manner consistent with scientific principles as well as practical considerations.

- (1) Will the application of the nanoemulsion (10% ALA gel), in the absence of occlusion, still achieve significant inflammation and lesion clearance?
- (2) Will shortened incubation times of Ameluz still achieve significant inflammation and lesion clearance?
- (3) Will the new test regimens achieve reduced pain during illumination?
- (4) Will the new test regimens be safe?

Consideration and discussion about the rationale for how we developed the proposed short-contact protocols, in relation to each scientific question, is provided below:

(1) Will the nanoemulsion (ALA gel) still work in the absence of occlusion?

Answer: Because the 10% ALA gel has much better penetration than 5-ALA/Kerastick that was shown to work without occlusion, it seems highly likely that 10% ALA gel will penetrate lesions and accumulate sufficient PpIX even in the absence of occlusion.

(2) Will short 10% ALA gel incubation times still achieve significant inflammation and lesion clearance?

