5.0 REGISTRATION

5.1 Recruitment

This study will be introduced to patients who meet eligibility criteria during their routine PDT visits and will either be provided a copy of the consent form to take home and review or give permission to be contacted for more information regarding the study. If the study coordinator is available, they will briefly meet with the patient to provide copy of informed consent form and explain study design, and the patient will be instructed to review consent form and call study coordinator with any questions and/or if they would like to move forward with participation. If the study coordinator is not available to meet with the patient during their routine visit, they will be notified and will call the patient to explain the study, and will also send a copy of the consent form via mail or email to the patient to review. If the study is not introduced to the patient, but they are eligible, the study coordinator can send a copy of our recruitment letter to patient via mail or MyChart to be followed up by a phone call. Recruitment will also be aided by IRB-approved advertisements posted in the Dermatology waiting room or other approved locations.

5.2 Consent:

Once the patient reviews the copy of the consent form that was provided by the study coordinator, either in person or via mail or email and the patient expresses interest in participating he/she will be scheduled for the first study visit. Once the patient arrives in clinic, the study will be explained once again, along with the chance to ask additional questions, and if the patient indicates continuing willingness then he/she will sign the consent form and be considered enrolled.

5.3 Randomization:

Upon enrollment, each patient will be assigned to one of the three treatment regimens (A, B, or C) using a block-randomization scheme that will be generated by staff in the Research Pharmacy (Investigational Drug Service) of the Cleveland Clinic; this assignment will insure an equal distribution of study patients across the 3 groups.

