11.0 STUDY PARAMETERS AND DETAILED STUDY CALENDAR

Details of 10% ALA application and red light treatment were described in detail under Section 6.0, “Treatment Plan”. The timing of visits is summarized below and in section 11.5 (“Calendar”).

11.1 **PDT treatment (Visit 1)**

All AK lesions are measured clinically and photographed. The clinician applies 10% ALA gel to entire face, without occlusion, and allows it to incubate if for either 10 min, 20 min, or 60 min, depending upon the study arm assignment. The patient will then be exposed to red light (BF-RhodoLED® device) for either 10 min or 20 min, as per the assigned study arm.

11.2 **Post-treatment assessment of side-effects (Visit 2)**

The patient will return at day 3 (± 1 day) for facial photographs to document their erythema reaction. They will also be asked about their side-effects, and insure that they know to fill out the side-effects questionnaire during the 6 days post-PDT.

11.3 **PDT treatment (Visit 3)**

This will occur 8 weeks (± 1 week) after Visit 1. All AK lesions will be measured clinically and photographed and if any remain, then the same PDT treatment regimen used at Visit 1 will be employed again here for a second round of treatment.

11.4 **Final observation (Visit 4)**

This will occur 3-6 months after Visit 1. The subject will return for final skin exam, lesion counts, and photography. A patient satisfaction questionnaire will also be administered at this visit. The large scheduling visit window is designed to maximize the likelihood of patient compliance, since many patients with AK are retirees who spend many months traveling and spend their winters in warmer climates far from Cleveland.

11.5 **Study Calendar**

CALENDAR. Timeline of procedures for patients enrolled in the study.

	VISIT 1 PDT treatment session #1	VISIT 2 Photos of skin redness	VISIT 3 PDT treatment session #2	VISIT 4 Final lesion counts
Scheduled visit: → Procedure: ↓	Day 1	Day 3 ± 1 day	Week 8 ± 1 week	Month 3-6
Sign informed consent	X			
Examine patient, mark each lesion with a pen, and count the lesions	X		X	X
Take photographs in our professional studio (frontal view and side views) to document inflammation.	X	X		
Take photographs using clinic iPhone camera to document lesion counts (pen-marks)	X		X	X

Apply topical ALA gel and incubate for 10, 20, or 60 min prior to turning on the light source (as per assigned study arms A, B, or C, respectively)	X		X	

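### The only washout (4.2.2) covers topical AK treatment; facial cryotherapy has none and PDT is unclear, so lesions already resolving at Visit 1 could be credited to the study regimen

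*Combined protocol and SAP*

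**What the plan says.** **Washout.** Section 4.2.2 excludes patients "Using any topical treatment on their AKs; must stop at least one month prior". No other criterion concerns earlier treatment of AKs. The nearest, 4.2.3, reads "Currently undergoing treatment for other cancers with medical or radiation therapy" and does not reach AK treatment.

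**How treatments are classed.** Section 1.1 sets out the alternatives as "surgical (cryotherapy, scalpel excision) and medicinal approaches (topical 5-fluorouracil, imiquimod, diclofenac cream) approaches, a relatively new modality called photodynamic therapy". Cryotherapy is therefore surgical, and only the drugs are called topical. The same section describes PDT as applying a topical drug to the lesions, and Section 9.1 classifies Ameluz as a topical agent.

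**Recruitment.** Section 5.1 begins: "This study will be introduced to patients who meet eligibility criteria during their routine PDT visits". It also allows letters, electronic messages, telephone calls and advertisements. Section 1.3 says "We plan to invite patients who are already scheduled to undergo PDT treatment in" the investigator's clinic. Section 5.2 has the interested patient scheduled for a first study visit, with no minimum gap since earlier treatment.

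**Baseline and endpoint.** Section 4.1 asks for ten or more facial lesions, and Section 6.1 counts them at Visit 1. Section 12.0 takes efficacy from the count that follows the second session. Sections 14.1 and 14.2 compare clearance with the published 3-hour regimen.

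**Timing of response.** Section 1.2 describes PDT as "triggering a somewhat delayed yet highly effective inflammatory-immunological response to eliminate the lesions". Section 11.3 schedules the next lesion count and possible retreatment thus: "This will occur 8 weeks (± 1 week) after Visit 1".

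**The concern.** Clearance is measured from the Visit 1 count. If some of those lesions are already on their way out because of earlier cryotherapy or PDT, they will be gone by the final count and will be scored as cleared by regimen A, B or C.

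Among the three randomised arms this balances in expectation, though with 10 patients per arm a chance imbalance is possible. The stated non-inferiority hypothesis, however, compares each regimen with a published result. Randomisation within this trial does nothing for that comparison. Credit for earlier treatment would raise observed clearance and make non-inferiority easier to conclude. If the type and date of the last treatment are not recorded at entry, the problem would also be hard to diagnose afterwards.

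**Working it through.** **1. What 4.2.2 reaches.**

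| Earlier facial treatment | Covered by 4.2.2? | Interval |
|---|---|---|
| Topical drugs | Yes | One month |
| Cryotherapy, excision | No, classed as surgical in 1.1 | None |
| ALA-PDT | Not stated; arguable, since it applies a topical drug | One month if covered, none if not |

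A patient treated recently with cryotherapy who still has ten facial lesions is eligible on any reading. A patient treated recently with PDT is eligible on one reading, and after one month on the other.

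**2. Inputs for the size.** The plan gives no carry-over figure, so there is none to reproduce. From Section 14.2 I take 61% clearance after one treatment (short regimen), 78% for the published 3-hour regimen, a margin of 25 points, and 97.1% after two treatments with 1-hour Ameluz and blue light. Two quantities are assumptions: f, the share of an exposed patient's baseline lesions that would clear anyway, and the share of an arm that is exposed.

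**3. Formula.** With true clearance c, observed clearance = f + (1 − f) × c, so the shift is f × (1 − c). This applies to mean lesion clearance, the scale used in Section 14.2, and not directly to the 75% and 100% clearance endpoints of Section 12.0.

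**4. Which c to use.** The 61% follows one treatment, but the endpoint follows two. If two sessions acted independently at 61% (an assumption), c = 1 − 0.39² = 84.8%. The blue-light figure gives c = 97.1%.

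**5. Shift in an exposed patient, in points.**

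| f | c = 61% | c = 84.8% | c = 97.1% |
|---|---|---|---|
| 10% | 0.10 × 39 = 3.9 | 0.10 × 15.2 = 1.5 | 0.10 × 2.9 = 0.3 |
| 20% | 7.8 | 3.0 | 0.6 |
| 30% | 11.7 | 4.6 | 0.9 |

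At c = 61%, observed clearance becomes 64.9%, 68.8% or 72.7%, and the 17-point gap to 78% narrows to 13.1, 9.2 or 5.3 points.

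**6. Shift in an arm mean.** If half the arm is exposed, the values halve: about 2.0 to 5.9 points at 61%, 0.8 to 2.3 at 84.8%, and at most about 0.4 at 97.1%. Against the 25-point margin, the upper ends are 5.85/25 = 23%, 2.3/25 = 9% and under 2%.

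**7. Direction.** The formula assumes that the other lesions respond at the full rate c. If lesions that survived earlier treatment are more resistant and clear at c′ instead, the shift vanishes when c′ = (c − f)/(1 − f). For c = 61% and f = 20%, that is 0.41/0.80 = 51%. Below that, the bias reverses.

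**The case against.** The strongest reply is that 4.2.2 probably covers PDT already. It speaks of any topical treatment, and the protocol itself calls Ameluz a topical agent. That is a fair reading and perhaps the more natural one. It leaves cryotherapy without a washout and leaves the PDT interval to each reader's interpretation.

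Second, exposure is not shown. A reader might infer from recruitment at PDT visits that the typical entrant has just had facial PDT. The documents do not support that. Section 1.3 describes patients awaiting PDT, Section 5.1 lists several other routes, and Section 14.3 describes the clinic's red-light AK patients as treated on the limbs. No passage says how common recent cryotherapy is. Baseline lesions must also show redness, scale and a gritty feel, which limits the entry of largely resolved ones.

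Third, a reader might infer from the week-8 visit that one month is demonstrably too short. It is not evidence of that. Week 8 is the retreatment visit, no passage shows clearing between weeks 4 and 8, and the description of the response as delayed carries no time scale. These passages give the investigators a reason to justify the interval, not a required length.

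Fourth, the 61% base overstates the shift for an endpoint read after two treatments. This stands, and the smaller columns above reflect it.

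**Conclusion.** The gap in 4.2.2 is real: cryotherapy and other procedural treatment of the face have no washout, and the status of PDT is undefined. The criterion as written can admit a patient whose baseline count is still falling from earlier treatment. In the comparison with the published regimen, that effect need not cancel; the documents do not give the published trials' own entry rules.

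The size is uncertain. For an assumed f of 10–30% in an exposed patient it is about 4–12 points at one-treatment clearance of 61%, about 1.5–4.6 points if two-treatment clearance is near 85%, and under 1 point if it is near 97%. The effect on an arm scales with the share exposed, which is unknown. It would be tempting to conclude that clearance will be inflated by the larger figures, or that the non-inferiority result is invalid. The documents support neither: both f and exposure are assumed, and resistant surviving lesions could offset or reverse the shift. This is an inexpensive improvement worth making before enrolment, not a demonstrated bias.

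**What to change.** Reword 4.2.2 to cover any AK-directed treatment of the face, naming topical agents, PDT, cryotherapy and other procedures, and tie the interval to Visit 1. The investigators should set the length and reconcile it with the protocol's own 8-week recount and its account of a delayed PDT response.

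Add to the screening procedure (Section 3.4) a field for the type and date of the last facial AK treatment. Ask the patient directly, since Section 10.0 limits the medical information gathered to the routine PDT note and study notes, and some recruits may have been treated elsewhere. Use the field to describe balance across arms. With 10 patients per arm, outcome comparisons by earlier treatment would be too thin to interpret.

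The cost is a short amendment, one added form item and slightly slower accrual, because some patients would wait longer before Visit 1.

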4.3 Inclusion of Women, Children, and Minorities

Men and women at least 18 years of age of any ethnic group are eligible for this trial, as long as they fulfill the eligibility criteria.

5.0 REGISTRATION

5.1 Recruitment

This study will be introduced to patients who meet eligibility criteria during their routine PDT visits and will either be provided a copy of the consent form to take home and review or give permission to be contacted for more information regarding the study. If the study coordinator is available, they will briefly meet with the patient to provide copy of informed consent form and explain study design, and the patient will be instructed to review consent form and call study coordinator with any questions and/or if they would like to move forward with participation. If the study coordinator is not available to meet with the patient during their routine visit, they will be notified and will call the patient to explain the study, and will also send a copy of the consent form via mail or email to the patient to review. If the study is not introduced to the patient, but they are eligible, the study coordinator can send a copy of our recruitment letter to patient via mail or MyChart to be followed up by a phone call. Recruitment will also be aided by IRB-approved advertisements posted in the Dermatology waiting room or other approved locations.

5.2 Consent:

Once the patient reviews the copy of the consent form that was provided by the study coordinator, either in person or via mail or email and the patient expresses interest in participating he/she will be scheduled for the first study visit. Once the patient arrives in clinic, the study will be explained once again, along with the chance to ask additional questions, and if the patient indicates continuing willingness then he/she will sign the consent form and be considered enrolled.

5.3 Randomization:

Upon enrollment, each patient will be assigned to one of the three treatment regimens (A, B, or C) using a block-randomization scheme that will be generated by staff in the Research Pharmacy (Investigational Drug Service) of the Cleveland Clinic; this assignment will insure an equal distribution of study patients across the 3 groups.

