6.0 TREATMENT PLAN

6.1. Overall descriptive narrative

At the first visit (Visit #1) (Day 1), informed consent will be obtained before starting any study procedures. AK lesions will be counted by [name] and his personally-supervised CCLCM medical student researcher using clinical criteria that include presence of a visible lesion with erythema (pink or red), presence of scale, and a gritty consistency by feel (palpation). Each identified lesion will be marked with a black pen. All the marked lesions will then be counted. As a back-up, the patient's face will be photographed with all the pen-marks in place, for later independent confirmation of lesions counts.

Photographs will be taken two ways. First, documentation of the pen-marked lesions on the face will be taken using CCF i-Phones that are routinely used in our clinic; these digital photographs will be transferred and stored directly in each study patient's electronic (Epic) record.

Second, for photographic documentation of inflammation, the patient will also be photographed by a professional photographer using standardized lighting and multiple views to document the degree of inflammation at baseline.

The skin will be degreased with an alcohol wipe, lesions gently abraded with fine sandpaper, and a thin layer of ALA gel (Ameluz®) will be applied to the entire face. No occlusive dressing will be used. For patients in group **A**, the ALA gel will be left on for 10 min, and then positioned in front of the red light and exposed for 20 min; this is a (10 + 20) regimen. Patients in group **B** and group **C** will receive a (20 + 10) regimen or (60 + 10) regimen, respectively.

Pain will be assessed by asking the patient to rate their perceived pain level on an 11-point VAS scale (0= no pain, 10 = intolerable pain). Patients will be asked to report their VAS score at 1 minute after red light begins, and at the 5 minute mark (when the RhodoLED beeps). They will be asked for a final VAS score immediately after the light is turned off.

To assess side effects, patients will receive a 6-day questionnaire to record their side-effects daily during the coming week, and which asks them to confirm that they completely avoided any sun exposure during the first two days after PDT. Patients will also receive a standard set of instructions for home aftercare that includes Aquaphor emollient, a topical steroid if necessary for comfort, and instructions to wear sunscreen and avoid sunlight for 48 hr.

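### Arm assignment is tied to signing consent, ahead of the Visit 1 lesion count, so the clearance denominator can be set with the arm already known

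*Combined protocol and SAP*

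**What the plan says.** Section 5.2 defines enrolment: at the first study visit, a willing patient means that "he/she will sign the consent form and be considered enrolled". Section 5.3 ties allocation to that moment: "Upon enrollment, each patient will be assigned to one of the three treatment regimens". The block scheme comes from the Research Pharmacy.

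Section 6.1 says that at Visit 1 "informed consent will be obtained before starting any study procedures". It then describes marking and counting, photography, gel and light. Counting is by the investigator and "his personally-supervised CCLCM medical student researcher using clinical criteria", namely visible redness, scale and a gritty feel. Photographs are taken once the pen marks are on, "for later independent confirmation of lesions counts".

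On eligibility, Section 4.1 requires patients "with a minimum of 10 actinic keratoses lesions on the face". Section 5.1 says "This study will be introduced to patients who meet eligibility criteria during their routine PDT visits", and Section 3.4 lists a screening step that may be done by telephone. Neither section prescribes a lesion count at that stage.

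The study calendar (Schema and Section 11.5) has rows for consent, marking and counting, and treatment. It has no row for randomisation.

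**The concern.** Percent clearance is a ratio whose denominator is the Visit 1 count. Randomisation balances the arms on what is fixed before allocation, but it does not protect a judgement made afterwards by someone who may know the arm. If borderline spots are marked more freely in one arm, and those spots tend to be gone at follow-up, that arm's clearance rises with no difference in treatment effect. Clearance is a primary endpoint, and each arm has 10 patients, so a small systematic shift is not diluted by numbers.

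The 10-lesion criterion has a related weakness. If the formal count is the first to show fewer than 10 lesions, the patient has already been assigned, and the plan does not say what happens next.

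**Working it through.** **Order of steps.** Enrolment is the signing of consent (5.2). Assignment is at enrolment (5.3). Consent precedes every study procedure, and the lesion count is described after it (6.1). Together these give consent, assignment, count, gel. I found no passage that holds the allocation until the count is recorded, conceals it from the counters, or masks them. The photographs show marks already placed. They allow the marks to be recounted, but they cannot show whether a borderline spot should have been marked, since one criterion is touch.

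**Effect of extra marks.** The plan gives no figure on this point, so what follows is illustrative. Let *n* be the true baseline lesions, *c* the true clearance and *k* the extra baseline marks absent at follow-up. The residual count is *n*(1 - *c*), so

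apparent clearance = 1 - *n*(1 - *c*)/(*n* + *k*), and gain = (1 - *c*) × *k*/(*n* + *k*).

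With *k* = 2 (assumed), for *n* = 10 (the eligibility minimum) and *n* = 20 (assumed):

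| True clearance | Source | Gain, *n* = 10 | Gain, *n* = 20 |
|---|---|---|---|
| 61% | 14.2, 1-hour planning value, one treatment | 0.39 × 2/12 = 6.5 points | 0.39 × 2/22 = 3.5 |
| 70% | assumed | 0.30 × 2/12 = 5.0 | 0.30 × 2/22 = 2.7 |
| 94.9% | 14.2, cited blue-light study, Levulan, two treatments | 0.051 × 2/12 = 0.9 | 0.051 × 2/22 = 0.5 |
| 97.1% | 14.2, same study, Ameluz, two treatments | 0.029 × 2/12 = 0.5 | 0.029 × 2/22 = 0.3 |

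**Responder endpoints, read per patient.** With 3 of 10 lesions left, clearance is 7/10 = 70%. Two vanishing extra marks make it 9/12 = 75%, which reaches the Section 12.3 threshold if exactly 75% counts; Section 12 does not say. Under 12.2 (100% clearance) the patient fails either way, because 3 lesions remain.

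**Direction.** If the two extra marks persist, the same patient scores 7/12 = 58%. The gain therefore requires that they vanish.

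**Consequence for a non-inferiority test between two randomised arms.** Inputs from Section 14.2 are 10 per group, SD 13, margin 25 points, true difference 10 points and two-sided alpha 0.05. The stated 80% power reproduces at one-sided 0.05 (79.9%, noncentral t, 18 df). At one-sided 0.025, the usual reading of two-sided 0.05, it is 68.5%. That is a separate matter.

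Taking one-sided 0.025, the standard error is 13 × √(2/10) = 5.81. For a bias *b* favouring the tested arm, the false non-inferiority rate at the margin is Φ(*b*/5.81 - 1.96):

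- *b* = 0: 2.5%
- *b* = 2: Φ(-1.62) = 5.3% (5.1% by noncentral t)
- *b* = 5: Φ(-1.10) = 13.6% (12.6% by noncentral t)

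Section 14.2 also discusses an SD of 30. The standard error is then 30 × √(2/10) = 13.42, and *b* = 5 gives Φ(5/13.42 - 1.96) = Φ(-1.59) = 5.6%. These are average biases across an arm. A 5-point value would need, for example, two vanishing extra marks in every patient of one arm and none in the other, at 70% clearance and 10 lesions each.

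**The case against.** The strongest reply is that the order is inferred rather than stated. Enrolment fixes no exact minute, the plan does not say when the pharmacy discloses the arm, and both Section 6.1 and the calendar list counting before any arm-specific step. The clinic may well count first. This stands as a caution about practice. It does not supply a safeguard, because the text as written permits the weaker order and most naturally describes it.

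Three stronger readings are tempting, and the documents do not support them:

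- *Eligibility is checked only after assignment.* Sections 5.1 and 3.4 put a screen before consent, and Section 1.3 draws on patients already scheduled for facial PDT. What remains is that no count is prescribed at screening, and a telephone interview cannot apply criteria that need palpation.
- *The counters are unmasked.* Section 6.1 says who counts, not what they know. Masking is unstated, and knowledge of the arm is possible but not shown.
- *The bias is material and runs one way.* Nothing shows that staff would mark differently by arm or which arm they would favour. The final efficacy outcome is after two treatments (Section 12), and at the cited two-treatment rates the effect is under 1 point against a 25-point margin.

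It is also fair to say that Section 14.1 compares the short regimens with the standard 3-hour regimen, known here only from published results. Over-marking in every arm would inflate that comparison whatever the allocation order. The point matters for contrasts among A, B and C. Section 1.3 calls C a control, and the sample-size statement compares each intervention with a control group, so such contrasts are in view.

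**Conclusion.** The point holds in a limited form. Sections 5.2, 5.3 and 6.1, followed as written, set the denominator of percent clearance after allocation, with no stated concealment or masking. The only prescribed count that could confirm at least 10 lesions falls in the same place, although a screen comes before it.

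The size cannot be fixed from the documents. For two vanishing extra marks it runs from about 0.5 points (97.1% clearance) to 6.5 points (61%) with 10 lesions, and is smaller with more lesions. It rests on the extra marks vanishing and on marking that differs by arm. The 75% endpoint is exposed; per-patient 100% clearance is not. This is a correctable gap in protecting a primary endpoint, not evidence that the counts will be biased.

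**What to change.** In Sections 5.3 and 6.1, set the Visit 1 order as:

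1. consent;
2. mark, count and photograph the lesions;
3. record and lock the count, and confirm at least 10 lesions;
4. release the allocation from the Research Pharmacy.

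The cost is one sentence in each section and a short wait for the allocation at Visit 1. No visits or patients are added, and the sample size does not change.

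The change protects the baseline count in comparisons between the randomised arms only. The comparison with published 3-hour results, and the Visit 3 and Visit 4 counts, for which no masking is described, stay as they are.
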